Safety, adherence, and resistance were evaluated in a single-arm, open-label clinical trial (ATN113) in which 67 HIV-1 uninfected adolescent MSM received Truvada once daily for PrEP {[Hosek et al 2017](#)}. The mean age of subjects was 17 years (range 15 to 18 years); 46% were Hispanic, 52% black, and 37% white. No new adverse drug reactions (ADRs) were identified in Study ATN113.

In Study ATN113, no seroconversions occurred in any subject who had tenofovir diphosphate (TFV-DP) levels associated with protection against rectal HIV exposure. HIV seroconversion occurred in 3 subjects: 2 subjects with TFV-DP levels below the limit of quantitation and 1 subject with TFV-DP levels that correlate with < 2 doses per week on average (< 350 fmol/sample). No tenofovir- or emtricitabine-associated HIV-1 resistance mutations were detected in the 3 seroconverters. The incidence rate for new HIV infections (seroconversion) is 6.4% (6.4 per 100 person-years). Adherence in adolescents in Study ATN 113 was assessed by dried blood spot, which demonstrated that 55% of adolescents 15 to 17 years of age at Week 12 had dried blood spot TFV concentrations of > 700 fmol/punch, consistent with taking at least 4 Truvada tablets per week.

The Amsterdam PrEP demonstration project reported that in 269 adults (≥ 18 years) taking Truvada for PrEP on a daily basis and followed for up to 2 years, the incidence rate for new HIV infections (seroconversion) is 0.4% (0.4 per 100 person-years) {[Hoorneborg et al 2019](#)}.

Data on the use of Truvada for PrEP in adults have been generated from controlled clinical studies and more recently in observational studies and PrEP demonstration projects. Data on the use in adolescents and young adults are however limited. This registry is designed to collect real-world data on use of Truvada for PrEP in adults and adolescents in Europe.

7.2 Rationale for differences to Non-Interventional Study Design Requirements This registry will have a focused safety data collection approach, as specified below, to meet the key objectives of the registry without adding additional overhead data collection with limited scientific value for the purposes of the registry. Gilead has requested a waiver from standard collection of AEs for this noninterventional post-authorization safety study (PASS), which was agreed upon by PRAC

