9. RESEARCH METHODS

9.1. Study Design

This is a prospective, longitudinal, observational, and voluntary participation registry designed to characterize the real-world use of Truvada for PrEP to prevent HIV-1 infections in adults and adolescents in Europe. The individuals who agree to participate in the registry will receive treatment solely based on current clinical practice in the country in which they reside. The use of Truvada for PrEP should be within the conditions of its approved SmPC. However, Gilead will not influence decision making by the participating HCPs or restrict enrollment into the registry to those individuals who are not receiving drug in full compliance with the SmPC (where local regulations allow to do so) as the objective of the registry is to describe the patterns of use and monitoring in real life. Data on intermittent use of Truvada for PrEP will be collected in countries permitting such data collection.

Both male and female adults and adolescents will be recruited for enrollment in the registry. Individuals who started Truvada for PrEP prior to first presenting to the participating HCP or are prescribed Truvada for PrEP will be eligible for enrollment. Baseline will be considered as the start date of Truvada for PrEP. The data for individuals receiving Truvada for PrEP prior to enrollment will be collected retrospectively from the individual's medical record.

Individuals will be followed while on Truvada for PrEP and the frequency of clinic visits will be at the discretion of the prescribers. Individuals will be followed until they are either lost to follow up, discontinued Truvada for PrEP, become infected with HIV, withdraw consent, or registry closure.

Details on Truvada for PrEP use, the healthcare Institution characteristics, and prescriber characteristics will also be collected .

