9.3.5. Variables Collected in the Event of Discontinuation of PrEP

The reason for and the date of PrEP discontinuation will be collected. If the reason for discontinuation is related to a serious adverse drug reaction (SADR) or treatment-related renal or bone adverse reactions, this will be collected in the AE section of the eCRF. If the discontinuation is due to a withdrawal of consent, no further data will be collected. If the discontinuation is due to development of a new HIV-1 infection (ie, seroconversion), the results of any HIV diagnostic testing and genotypic resistance testing should be reported both in the registry and to the applicable country central database for HIV testing and diagnosis. Information on adherence to Truvada for PrEP along with possible factors leading to HIV-1 seroconversion should be reported.

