9.5. Study Size

The purpose of the registry is to provide insight into the patterns of Truvada for PrEP usage and how clinicians are monitoring individuals on Truvada for PrEP. The registry is not designed or powered to compare rates of seroconversion or adherence with studies or demonstration projects.

Enrollment will be open to both adults and adolescents, and enrolled individuals will be followed while Truvada for PrEP is continued. Target is to enroll and follow enough adults to provide at least 400 person-years of follow-up data and enough adolescents to provide at least 25 person-years of follow-up data.

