11.1.1. Safety Information to be Collected

Safety information is required to be collected and reported for this registry from the time of the patient's consent to participate in the registry (ie, signing informed consent) until up to 4 weeks after completion of Truvada for HIV-1 PrEP or early discontinuation of Truvada, loss of follow-up, or withdrawal of consent. Safety information to be collected includes a description of the AE, start and stop dates, severity, causality, and other relevant medical information.

The safety profile for Truvada has been well characterized in clinical studies and post marketing experience. Considering the main goal of this registry, aiming to achieve consistency and simplicity in data collection and reporting without undue burden on the investigators, this registry is designed to collect and analyze the following safety information in individuals taking Truvada for PrEP:

- Fatal Events
- All SADRs
- Treatment emergent renal or bone ADRs
- Pregnancy reports (maternal pregnancy and partner pregnancy)

Timelines for reporting to the registry are as follows:

- Within 3 calendar days of knowledge of all fatal Events (regardless of causality) and SADRs
- Within 30 calendar days of treatment emergent renal or bone ADRs
- Within 30 calendar days of knowledge of a pregnancy

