11.5. Assessment of Causality for Study Drugs

The investigator or qualified sub-investigator is responsible for assessing the causal relationship to drug therapy for each event and using clinical judgment and the following considerations:

- **No:** Evidence exists that the AE has an etiology other than the drug. For SAEs, an alternative causality must be provided (eg, preexisting condition, underlying disease, intercurrent illness, concomitant medication).
- **Yes:** There is a reasonable possibility that the event may have been caused by the medicinal product (and thus reported as an ADR or an SADR).

It should be emphasized that ineffective treatment should not be considered as causally related in the context of reporting safety information.

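### No site is required to record an HIV test or genotype obtained after Truvada is stopped for another reason, so infections acquired on the drug can go uncounted

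*Protocol*

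**What the plan says.** Section 9.1 sets the end of follow-up: "Individuals will be followed until they are either lost to follow up, discontinued Truvada for PrEP, become infected with HIV", with consent withdrawal and registry closure as the remaining end points. Section 9.5 agrees: "enrolled individuals will be followed while Truvada for PrEP is continued".

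At discontinuation, 9.3.5 collects the reason and the date. HIV and resistance results appear there in one branch: "If the discontinuation is due to development of a new HIV-1 infection (ie, seroconversion), the results of any HIV diagnostic testing and genotypic resistance testing" are then to be reported. Nothing comparable is asked of people who stop for another reason.

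Table 9-1 places HIV tests at baseline and at follow-up visits, both under the on-treatment heading, and in a separate seroconversion column. It has no post-discontinuation visit.

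Section 11.1.1 does reach past the last dose, "until up to 4 weeks after completion of Truvada for HIV-1 PrEP or early discontinuation of Truvada, loss of follow-up, or withdrawal of consent", but its list is fatal events, SADRs, renal or bone ADRs and pregnancies. A new infection cannot enter as an ADR or SADR through lack of effect, because 11.5 says "ineffective treatment should not be considered as causally related in the context of reporting safety information".

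Section 8 nevertheless makes new HIV diagnoses and Truvada resistance an objective, and 9.7 promises a seroconversion rate with a 95% confidence interval. The only person-time definition, in 9.3.1, runs from PrEP initiation to the PrEP end date.

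**The concern.** Take a person who becomes infected while on Truvada, has not yet had a positive test, and stops for cost, side effects or perceived low risk. If the diagnosis comes a few weeks later, no passage obliges the site to enter it. The on-drug days remain in the denominator, the event is absent from the numerator, and any genotype is not captured. This mechanism can act in one direction only: towards fewer infections and fewer resistance findings.

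This is a data-collection gap, so an analysis plan cannot close it afterwards: results that were never entered cannot be analysed. The protocol follows selected adverse reactions for weeks after the last dose, and adverse pregnancy outcomes after the study (11.1.3), but makes no such provision for HIV. Section 9.9 does not list the problem among the limitations.

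**Working it through.** The protocol gives no precision calculation and no derivation of its person-year targets, so there is no stated figure to reproduce.

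**1. Expected cases at target size.** Inputs are the targets in 9.5 and the rates cited in 7.1.
- Adults: 400 PY × 0.4/100 PY = 1.6 cases.
- Adolescents: 25 PY × 6.4/100 PY = 1.6 cases.

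**2. Width of the interval at such counts** (exact Poisson, rate per 100 PY).

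| Cases | Adults, 400 PY | Adolescents, 25 PY |
|---|---|---|
| 0 | 0 (0 to 0.92) | 0 (0 to 14.8) |
| 1 | 0.25 (0.006 to 1.39) | 4.0 (0.10 to 22.3) |
| 2 | 0.50 (0.06 to 1.81) | 8.0 (0.97 to 28.9) |

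**3. Share of on-drug infections missed.** With a constant hazard, share = q × u / T, where q is the proportion who stop for a non-HIV reason, u the time from the last informative HIV test to the stop, and T the mean exposure. The protocol gives none of these, and 9.1 leaves visit frequency to the prescriber. Assumed ranges: q 25% to 75%, u 2 to 12 weeks, T 0.5 to 2 years. The formula also assumes that no site reports a post-stop diagnosis of its own accord.
- Low: 0.25 × (2/52.18)/2 = 0.5%.
- Mid: 0.50 × (6.5/52.18)/1 = 6.2%.
- High: 0.75 × (12/52.18)/0.5 = 34.5%.

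**4. Effect on the expected rate.**
- Mid: adults 0.40 × (1 − 0.062) = 0.375; adolescents 6.4 × (1 − 0.062) = 6.0 per 100 PY. About 1.6 × 0.062 = 0.1 case is lost in each group.
- High: adults 0.40 × (1 − 0.345) = 0.26; adolescents 6.4 × (1 − 0.345) = 4.2 per 100 PY. About 1.6 × 0.345 = 0.55 case is lost in each group.

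**5. If risk rises before the stop.** Suppose the hazard triples in the last 0.125 year of stoppers in the mid case (an assumption). The share missed becomes 0.5 × 3 × 0.125 / [0.5 × (0.875 + 3 × 0.125) + 0.5 × 1] = 0.1875/1.125 = 17%, still inside the range above.

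**The case against.** The strongest reply is that the protocol is open on this point and does not prohibit collection. The seroconversion column in Table 9-1 stands outside the on-treatment heading. The synopsis asks for seroconversion date, circumstances and resistance results with no condition on why PrEP stopped, and names discontinuation and seroconversion as separate collection points. Section 9.3.5 rules out further data only after withdrawal of consent. A reader might infer that such a person must be recorded as an HIV-free discontinuation; no passage says so. This stands, and it turns the charge from certain loss into possible and uneven loss.

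Some stoppers also stay observable. A test done at the stopping visit is captured as a follow-up visit, and 9.3.1 disregards short interruptions and allows later re-exposure. This stands too, but it does not help people who stop between tests and do not restart.

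A reader might infer that the rate is roughly halved, since losing one of two adult cases moves it from 0.50 to 0.25 per 100 PY. That is an illustration of a 50% loss, above even the high case, and the two intervals overlap widely.

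A reader might also take the adolescent study in 7.1 as proof that stopping is informative: "HIV seroconversion occurred in 3 subjects: 2 subjects with TFV-DP levels below the limit of quantitation", and the third had low levels. But the protocol's account says nothing about stopping, all three were detected, and none had tenofovir or emtricitabine resistance mutations. Informative stopping is plausible but is not shown.

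Finally, the registry is descriptive and, by 9.5, not designed to compare seroconversion rates. That limits the severity. It does not remove the objective of documenting new diagnoses.

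**Conclusion.** The gap is real in this form: follow-up ends at discontinuation, and nothing requires an HIV or genotype result to be recorded after a stop made for a reason other than HIV. The bias from this mechanism is downward. That direction follows from the text, reading the rate's denominator as the 9.3.1 person-time, because 9.7 names no other.

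The size does not follow from the text. It runs from under 1% to about a third of on-drug infections, near 6% in the mid case, and rests wholly on assumed test interval, stop rate and exposure. On average it is small beside the Poisson interval. It still deserves correction because so few cases are expected that a single missed one changes the reported result and may be the only source of resistance data, and because the remedy is cheap before data collection and impossible after it.

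**What to change.** Align 9.1, 9.3.5, Table 9-1 and 11.1.1. Unless consent is withdrawn, record the first HIV test available from routine records within a defined period after the last Truvada dose (date, method, result and any genotype), whatever the reason for stopping. Mandate no test and no visit, so the non-interventional design is kept.

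Report post-stop diagnoses as a separate category with last-negative and first-positive dates, and give the rate with and without them as a sensitivity analysis. Do not count them all as acquired on Truvada. If tests were every 3 months and stops fell at random between them, the gap between the last test before the stop and the first after it would average 1.5 months on drug and 1.5 months off. At constant hazard, about half of the added infections would then be wrongly attributed.

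Add a sentence on remaining under-ascertainment to 9.9. The cost is a protocol amendment and one short chart-based form. Some people will have no later test at the site, so the gap narrows but does not close.

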9.2. Setting

The registry population will consist of adults and adolescents who are HIV-1 negative and are taking Truvada for PrEP. Individuals who have either self-initiated Truvada for PrEP or have been prescribed Truvada for PrEP and are being monitored while on Truvada for PrEP will be informed about the registry by their HCPs at one of the participating sites. HCPs should assess all users of Truvada for PrEP for inclusion in the registry as they present at the clinic (routine clinic visit) and provide information on the registry if they feel the individual meets the inclusion criteria and does not meet the exclusion criterion. If the individual agrees to participate, they will be required to read, understand, and provide informed consent / assent prior to any registry data collection.

Representative healthcare institutions from countries where Truvada for PrEP are being reimbursed will be recruited to participate in this registry. To facilitate participation with HCPs and users of PrEP, Gilead will leverage its network of investigators who have been a part of prior clinical studies and/or demonstration projects in HIV treatment and PrEP including those doctors

who may not have participated in a study yet but have shown a willingness to learn more about HIV or about antiviral drugs use.

As a supplement to the above, Gilead will work with local key opinion leaders, professional medical organizations & societies and local medical groups who are experienced in the management of HIV infection and prevention (eg, infectious disease specialists).

As part of the registry set up activities, Gilead intends to contact local community groups regarding the registry for Truvada for PrEP.

Due to the restricted availability of Truvada for PrEP in various European countries, this registry will initially be conducted in a limited number of European countries where Truvada for PrEP is being reimbursed. Initially, the target countries to be included in the registry will be Belgium, France, Norway, Portugal, and Sweden. Other countries may be included following reimbursement approval of Truvada for PrEP. The registry will also collect data on HCPs who prescribe Truvada for PrEP.

Recruitment methods within each country will begin by assessing if they have a national policy for PrEP or a similar initiative that would support reimbursement of all HIV-1 PrEP medicinal products or only Truvada or generic equivalents products. HCPs who prescribe products for HIV-1 PrEP will be contacted to determine if they prescribe Truvada for PrEP and if so they will be invited to participate in the registry. Additionally, a review of planned, ongoing, or completed clinical studies or demonstration projects which include Truvada for PrEP will be carried out to identify potential individuals who have completed or discontinued participation in the study but continue to take Truvada for PrEP.

A written contract on the implementation of this registry shall be concluded between sponsor and clinical site. Personnel from the sponsor company or the contract research organization (CRO) will describe the registry to HCPs at each site and provide training on the registry design and data collection to ensure, as much as possible, quality and consistency of data collected. HCPs will only be compensated for their time and efforts on the registry based on current fair market value at the time of contract finalization.

9.2.1. Inclusion Criteria:

- HIV-1 negative adults and adolescents who are deemed to be at high risk for acquiring HIV-1
- HIV-1 negative adults and adolescents who provided consent / assent and, depending on local country regulations, parental or legal guardian permission to participate in the registry
- HIV-1 negative adults and adolescents who are receiving Truvada for HIV PrEP, either as a daily or intermittent regimen, and that are clinically monitored

9.2.2. Exclusion Criteria:

- Individuals currently participating in a clinical study of HIV PrEP

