for PrEP to prevent HIV-1 infection in adults and adolescents in Europe. Due to the restricted availability of Truvada for PrEP in various European countries, this registry will initially be conducted in a limited number of European countries where Truvada for PrEP is being reimbursed. Initially, the target countries to be included in the registry will be Belgium, France, Norway, Portugal, and Sweden. Other countries may be included following reimbursement approval of Truvada for PrEP. Within each of the countries where drug utilization will be assessed, representative healthcare institutions (where biomedical interventions for HIV prevention are being prescribed) and institutions with individuals who have discontinued participation in clinical studies or demonstration projects with Truvada for PrEP will be assessed for feasibility to participate in this registry which will focus on all individuals receiving Truvada for PrEP. This registry will not provide Truvada.

Both male and female adults and adolescents will be recruited for enrollment in the registry. Individuals who started Truvada for PrEP prior to first presenting to the participating healthcare professional (HCP) or are prescribed Truvada for PrEP will be eligible for enrollment. Individuals receiving Truvada for PrEP will be followed and relevant demographic and ongoing use data will be collected in the registry. The individuals who agree to participate in the registry will receive treatment solely based on current clinical practice in the country in which they reside. The use of Truvada for PrEP should be within the conditions of its approved SmPC. However, Gilead will not influence decision making by the participating HCPs or restrict enrollment into the registry to those individuals who are not receiving drug in full compliance with the SmPC (where local regulations allow to do so) as the objective of the registry is to describe the patterns of use and monitoring in real life. Data on intermittent use of Truvada for PrEP will be collected in countries permitting such data collection. The frequency of clinic visits will be at the discretion of the prescriber.

Details on the product prescribed, the healthcare institution characteristics, and prescriber characteristics will also be collected.

Country-specific protocols may be developed to comply with local regulations on data collection. Gilead will work with a contract research organization to develop and launch the registry.

Population:

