9.3.1. Exposure

Data on Truvada for PrEP will be collected. The start and stop dates will be used to estimate person-time of exposure to Truvada. Person-time of exposure will be defined as ([PrEP end date - PrEP initiation date] + 1), regardless of temporary interruptions in exposure (< 30 days) and will be expressed in days (recorded in whole days, eg, 41 days). Exposure starts the first day the medication was prescribed or self-initiated (and assumed to have been taken). An individual may have multiple exposures defined as the re-initiation of PrEP after a period of stoppage that is greater than 30 days. Aggregated person-time may also be expressed in person-years ([number of person days]/365.25). Individuals who are taking PrEP on an intermittent or event-driven basis will have exposure calculated in a similar fashion ([PrEP end date - PrEP initiation date] + 1).

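### For people who began Truvada inside a PrEP study or demonstration project, study time counts as real-world exposure, and no listed item lets it be separated out

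*Protocol*

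**What the plan says.** **Recruitment.** The Synopsis assesses for feasibility "institutions with individuals who have discontinued participation in clinical studies or demonstration projects with Truvada for PrEP". Section 9.2 adds a review of planned, ongoing and completed studies and demonstration projects to "identify potential individuals who have completed or discontinued participation in the study but continue to take Truvada for PrEP". The single exclusion criterion (Section 9.2.2) is "Individuals currently participating in a clinical study of HIV PrEP"; it does not address past participation.

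**Clock.** Section 9.1: "Baseline will be considered as the start date of Truvada for PrEP". It goes on: "The data for individuals receiving Truvada for PrEP prior to enrollment will be collected retrospectively from the individual's medical record". Section 9.3.1: "Person-time of exposure will be defined as ([PrEP end date - PrEP initiation date] + 1), regardless of temporary interruptions in exposure (< 30 days"), and "Exposure starts the first day the medication was prescribed or self-initiated (and assumed to have been taken"). A stop of more than 30 days opens a second exposure, but the first is kept.

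**Data items.** Section 9.3.3 describes the Table 9-1 items as routine-care data, as far as medical records hold them. The table records Truvada as prescribed or self-sourced, and prior PrEP as prescribed or self-medicated. It also records consent and the PrEP start and stop dates. It has no item for participation in an earlier study or the date of leaving one.

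**Other text.** The Synopsis (Variables) and Section 9.4 describe data collection after enrollment or during registry participation, which does not fit the retrospective collection in Section 9.1. Section 9.9 does not list earlier study participation among the limitations.

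**The concern.** Section 9.1 gives the registry's aim as describing use and monitoring in real life, and leaves visit frequency to the prescriber. In a trial or demonstration project, the project may set drug supply, visits and adherence support. The plan deliberately seeks people who come from such settings and then dates their exposure from the first Truvada tablet. Where that tablet was taken inside the study, the study period joins the registry's exposure.

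At stake are the summaries behind the first and third objectives: dosing pattern and duration of use, visit frequency, and adherence. A reader of the final report could not tell how much of each describes routine care, and on the listed items the analyst could not show it.

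**Working it through.** The protocol gives no number of former study participants and no study durations, so it has no figure on this point to reproduce. The 400 adult and 25 adolescent person-years in Section 9.5 are stated without derivation.

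**Step 1: apply the written rules to one person.** Take one year on Truvada in a demonstration project, no gap of 30 days or more, then one year in the registry. By Sections 9.1 and 9.3.1 this is one exposure of 2 years with baseline at project start. Half of it is study time. Someone who first took Truvada after leaving the study contributes none.

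**Step 2: share of counted person-time.** Let f be the share of participants who started Truvada in an earlier study, T their years on it there, and F the mean registry years per participant.

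Share = fT / (fT + F)

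Inputs:
- f: 10% to 50% (assumed).
- T: 0.5 to 2 years (assumed; Section 7.1 cites a demonstration project with follow-up of up to 2 years).
- F: 0.5 to 2 years. The 2 is the mean for uniform accrual over 3 years plus 6 months with no discontinuation, (3.5 + 0.5)/2. The lower values are assumed.

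| f | T | F | Calculation | Share |
|---|---|---|---|---|
| 10% | 0.5 | 2 | 0.05/2.05 | 2% |
| 25% | 1 | 2 | 0.25/2.25 | 11% |
| 25% | 1 | 1 | 0.25/1.25 | 20% |
| 50% | 2 | 0.5 | 1.00/1.50 | 67% |

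**Step 3: direction for visit frequency.** Take f = 25%, T = 1, F = 1 and an assumed routine rate of 2 visits per year, so counted time per participant is 1.25 years.
- Study visits at an assumed 4 per year, all in the record: (2 + 0.25 × 4)/1.25 = 2.4 per year.
- Study visits also at 2 per year, all in the record: (2 + 0.25 × 2)/1.25 = 2.0, no bias.
- Study time counted, but no study visits in the record: 2/1.25 = 1.6 per year.

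The bias can go up, vanish or go down, depending on what the medical record holds.

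**Step 4: the person-year target, if back-dated time were counted.** N = 400/(F + fT). With f = 25%, T = 1, F = 1: N = 400/1.25 = 320 adults, giving 320 routine-care and 80 study person-years; 400 routine-care person-years would need 400 adults. With F = 2: N = 400/2.25, rounded up to 178, with about 356 routine-care and 44 study person-years; 200 adults would be needed. Section 9.5 does not say whether back-dated time counts, so this step is conditional.

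**The case against.** Several objections have weight.

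- *Only routine-care data in the medical record are collected.* Section 9.3.3 says so, and Section 9.1 limits retrospective data to that record. A reader might infer that study visit schedules and adherence support pass wholesale into the summaries and push them upward; the text does not support that. They enter only as far as the record contains them. Exposure is different: it follows from two dates, so study time enters by formula.
- *The time can be removed.* A reader might infer that it can never be identified. But current study participants are barred at enrollment, so the time at issue precedes consent, and an analysis restricted to post-consent time would drop it. That stands, at a price: it also discards the retrospective routine-care time that Section 9.1 sets out to collect.
- *The start date may lie outside the study.* For some it will, and whether study-supplied drug counts as prescribed under Section 9.3.1 is not stated. Yet the people sought are those who continue Truvada after a study, so for some the start must be expected to lie inside it.
- *The analysis plan can split the time.* It could set the rule, but it needs a flag and an exit date, and Table 9-1 lists neither. The eCRF is to be built from that table (Section 9.6).
- *The exclusion criterion has another purpose.* A reader might infer that back-dating defeats it. The protocol gives no reason for the criterion. The remark in Section 7.2 that a clinical study's effect on behavior would run against the main objective defends the noninterventional classification and says nothing about past study time.
- *Moving baseline would do harm.* It would understate total Truvada duration and turn baseline eGFR and phosphate into on-drug values. This is right, and the fix leaves baseline where it is.

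**Conclusion.** The point holds for a defined group: people who started Truvada inside a PrEP study or demonstration project and carried on into the registry. For them, Sections 9.1 and 9.3.1 count study time as real-world exposure, and Table 9-1 has nothing to mark it. Study visits and adherence data follow to an unknown extent.

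The size cannot be derived from the protocol. The shares of 2% to 67%, with 20% in the middle case, rest on assumed values of f and T and mostly assumed values of F. The direction of bias in visit frequency and adherence is unknown. A reader might also infer that the 400 and 25 person-year targets are inflated; Section 9.5 speaks of follow-up data and does not say that back-dated time counts, so this is not shown.

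The change should be made before data collection, because a missing flag and exit date are hard to recover afterwards.

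**What to change.** - **Sections 9.1 and 9.3.1:** keep the Truvada start date as baseline for exposure history and laboratory values.
- **Table 9-1:** add an item for earlier participation in a PrEP study or demonstration project (yes/no) with exit date.
- **Sections 9.3.1 and 9.7:** count real-world person-time, persistence, adherence and monitoring frequency from the later of Truvada start and study exit. Report earlier study time separately, and show key results with and without these participants.
- **Section 9.5:** state that study time does not count towards the 400 and 25 person-years.
- **Synopsis (Variables) and Section 9.4:** reconcile with the retrospective collection in Section 9.1.
- **Section 9.9:** add earlier study participation as a limitation.

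The cost is one more eCRF item and somewhat less countable retrospective person-time. Recruitment is unchanged, and routine-care time before consent is kept.
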